7.9. **Will subjects be informed of results obtained from their DNA?** *Choose an item.*

7.10. Explain if the study is looking for an association between a genetic marker and a specific disease or condition, but at this point it is not clear if the genetic marker has predictive value.

7.11. Describe if the study is based on the premise that a link between a genetic marker and a specific disease or condition is such that the marker is clinically useful in predicting the development of that specific disease or condition.

7.12. Will the subject be notified of the results and the provision for genetic counseling? *Choose an item.*

Section 8: International Research

8.1. Does this study involve international research? **NOT APPLICABLE** If no, go directly to section 9.

Section 9: Statistical Analysis

9.1. **Include statistical power calculations and the assumptions made in making these calculations.**

This study has been powered for two phases of hypothesis testing. In the first phase, we will compare each of the two intervention arms to control. We estimate that a sample of 180 participants allocated in a 1:1:1 distribution, will ensure at least 80% power to detect a 900-step difference between each intervention arm and control, with a standard deviation of 1500 steps. This calculation assumes a 10% missing data rate and a conservative Bonferroni adjustment of the type I error rate with a 2-sided alpha of 0.025. In the second phase, we will compare successful intervention arms to each other. We expect that the magnitude of difference between intervention arms will be less than that of successful intervention arms compared to control. For this second phase of analyses will use a conservative Bonferroni adjustment of the type I error rate with a 2-sided alpha of 0.017 to adjust for up to 3 comparisons. In 2012, more than 57,500 veterans enrolled for care at CMCVAMC and comprised nearly 463,000 visits. Since 70% of veterans are overweight or obese, nearly 40,000 veterans may be eligible for this study. Based on this data and prior studies, we estimate that we can fill the study within 6 months. We will plan to oversample women and minorities in the recruitment process.

9.2. **Define plans for data and statistical analysis, including key elements of the statistical plan, stopping rules and endpoints.**

Data from the clinical trial will be analyzed using statistical software in SAS or R. In our primary analyses, we will multiple imputation for missing data and step values less than 1000. We will use linear mixed effects models to compare the change in mean daily step count from baseline to intervention period (weeks 5 to 12), adjusting for baseline step count and time. To test of the robustness of our findings we will also evaluate models using collected data without imputation. We will conduct similar models for the secondary outcome of change in mean daily steps from baseline to follow-up and use logistic models for the secondary outcomes of proportion of participant-days meeting goal during intervention and follow-up. All hypothesis tests will use a conservative Bonferroni adjustment as described in the power calculation.

9.3. **Provide sample size determination and analysis (include anticipated rate of screen failures, study discontinuations, lost to follow-up, etc.)**

See above.

9.4. **Describe how, where and by whom the data will be analyzed.**

The data will be analyzed by [name] and [name] with the help of CHERP faculty at the VA.

Section 10: References

1. Ischemic Heart Disease Quality Enhancement Research Initiative. U.S. Department of Veterans Affairs. June 2014. Available online at: http://www.queri.research.va.gov/about/impact_updates/IHD.pdf. Accessed January 26, 2017
5. Evidence-based Synthesis Program. The impact of wearable motion sensing technologies on physical activity: A systematic review. Department of Veterans Affairs Health Services Research & Development Service. September, 2015.

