Social incentives or those influences that impact individuals to adjust their behaviors based on social ties and connections have been demonstrated in retrospective studies to influence behavior but have not been well examined prospectively. Insights from behavioral economics can be used to design gamification interventions to enhance social incentives such as the support, competition, or collaboration but the optimal design to increase physical activity is unknown. This study will use behavioral economics frameworks to design and test a social incentive-based gamification intervention with and without financial incentives to increase physical activity among overweight and obese veterans. We will test whether this intervention can be conducted remotely, thereby reducing participant burden of coming in for an in-person visit and creating a more scalable intervention design. Specifically, we will test the ability of using wearable devices with social and financial incentive-based interventions to augment physical activity as measured by change in mean daily step counts which will be tracked by a wearable activity tracker.

Section 4: Objectives Section

4.1. Describe the study's purpose, specific aims, or objectives.

The objective of this study is to use a randomized, controlled trial to test the effectiveness using a remotely-monitored social incentive-based gamification intervention with and without financial incentives to increase physical activity among overweight and obese veterans. All participants will use wearable devices to establish a baseline step count and monitor their physical activity during the study.

Primary outcome: The primary outcome is change in mean daily steps from baseline to the weeks 5 to 12 of the intervention period (which excludes the 4-week ramp-up phase).

Secondary outcomes: Secondary outcomes include change in mean daily steps from baseline to the 8-week follow-up period, Proportion of participant-days achieving step goals during the intervention and follow-up periods.

Exploratory outcomes: We will explore how participant characteristics and behaviors are associated with strong or poor physical activity performance.

4.2. **State the hypotheses to be tested.**

Hypothesis: The combination of social and financial incentives will lead to greatest increase in mean step counts from baseline.

Section 5: Study Procedures

5.1. **Study Design**

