5.1.7.1.9. Justification that the data requested represent the minimum necessary to conduct the research.

5.1.7.1.10. A discussion of plans for obtaining informed consent and HIPAA Authorization, or for requesting the IRB to waive these requirements. If the investigator requests that the requirement for a HIPAA Authorization be waived, justification for this request must be included in information submitted to the IRB.

5.1.7.1.11. **In addition to the above, provide a Standard Operating Procedures Manual for the data repository. Contact IRB office for additional details.**

5.2. **Subject Recruitment Methods**

5.2.1. State how many subjects will be needed: 180 total subjects, with 60 in each arm of the study.

5.2.2. Who will be responsible for recruiting potential subjects? Provide titles of individuals.

The study team will include:

[name], MBA, MS – Principal Investigator
 [name] – Co-Investigator
 [name] – Project Manager
 [name] – Project Manager
 [name] – Clinical Research Coordinator
 [name] – Clinical Research Coordinator

5.2.3. **How will initial contact with potential subjects be made? (e.g., local clinics, physician referrals, letters to prospective subjects)**

Veterans receiving care at the CMCVAMC will be mailed a letter describing the study, and study contact information. They will have the ability to opt out from future communications if they like. If an individual is interested in the study, they will be given the opportunity to ask questions and instructed to sign up for the study on the Way to Health Platform. Then the veteran will be called to conduct oral consent and eligibility and baseline surveys. The study team will mail the veteran a copy of the consent form, a wearable device to track step counts and provide instructions to create an account by which they will transmit de-identified step data to the research team.

We have designed the study to be conducted remotely for recruitment, enrollment and the study design. This will allow Veterans to review the study and design in the comfort of their own homes with a member of the study team able to answer questions by phone. It will also reduce time burden any costs that would otherwise be placed on Veterans if he or she had to travel to the CMCVAMC for an in-person visit.

5.2.4. **Will you be using any of the following methods to recruit subjects? (Check all that apply.)**

N/A

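### The study is said to be powered for two phases, but 180 participants were sized for the comparisons with control only; Arm 3 versus Arm 2 needs about 932 to 945 steps for 80% power

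*Protocol*

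**What the plan says.** Protocol 5.1.1 (Accrual) and 9.1 carry the same paragraph. It begins "This study has been powered for two phases of hypothesis testing".

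- **First phase.** "We estimate that a sample of 180 participants allocated in a 1:1:1 distribution", it says, "will ensure at least 80% power to detect a 900-step difference between each intervention arm and control, with a standard deviation of 1500 steps". The calculation uses a two-sided alpha of 0.025 and allows for 10% missing data. Protocol 5.2.1 confirms the arm size: "180 total subjects, with 60 in each arm of the study".
- **Second phase.** "In the second phase, we will compare successful intervention arms to each other". The alpha is 0.017 two-sided, to cover up to three comparisons. On the size of effect the text says only: "We expect that the magnitude of difference between intervention arms will be less than that of successful intervention arms compared to control". It gives no difference in steps, no power and no sample size.

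Protocol 9.2 adds "All hypothesis tests will use a conservative Bonferroni adjustment as described in the power calculation". Protocol 9.3, on sample size, only refers back to the earlier text. The SAP contains no power statement. Protocol 4.2 gives the hypothesis: "The combination of social and financial incentives will lead to greatest increase in mean step counts from baseline".

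**The concern.** The second phase uses a stricter alpha than the first, expects a smaller difference and has no more participants per arm. At the same SD it cannot have the power stated for the first phase, yet the opening sentence claims power for both.

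The comparison matters. Under Protocol 5.1.1, Arms 2 and 3 play the same game and Arm 3 adds a loss-framed account of up to $120, so Arm 3 versus Arm 2 isolates what the money adds. The hypothesis in 4.2 needs that comparison as well as Arm 3 versus control. Neither document says how a non-significant second-phase result will be interpreted. A reader told that the study was powered for this test could take such a result as evidence that money adds nothing, and the stated design values do not support that reading.

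**Working it through.** **Inputs** (Protocol 9.1, repeated in 5.1.1): 60 per arm; 10% missing, so 60 × 0.9 = 54 evaluable per arm; SD 1500; difference versus control 900; two-sided alpha 0.025 (first phase) and 0.017 (second phase); power 80%. The second-phase SD and evaluable number are not stated, so the first-phase values are carried over.

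**Formulae** (normal approximation; noncentral t with 106 df as the second figure throughout):

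- Standard error of a difference: 1500 × √(2/54) = 288.7 steps.
- Detectable difference: (z for 1 − α/2 + z for 0.80) × standard error.
- Number per arm: 2 × (1500/difference)² × (z for 1 − α/2 + z for 0.80)².

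**Step 1: reproduce the plan's figure.** At alpha 0.025 the z sum is 2.241 + 0.842 = 3.083. The number per arm is 2 × (1500/900)² × 3.083² = 52.8, so 53 (t: 55). Dividing by 0.9 gives 59 (t: 62) per arm, or 177 (t: 186) in total, against the stated 180. With 54 per arm, power at 900 steps is 81.0% (t: 79.9%) and the detectable difference is 890 (t: 901). So 180 is a first-phase number with almost no reserve.

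**Step 2: second phase at the same values.** At alpha 0.017 the z sum is 2.387 + 0.842 = 3.228. The detectable difference is 3.228 × 288.7 = 932 steps (t: 945). Power at 900 steps is 76.8% (t: 75.5%). For 80% power at 900 steps, 58 (t: 60) evaluable per arm are needed; dividing by 0.9 gives 65 (t: 67) per arm, or 195 (t: 201) in total.

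**Step 3: sensitivity to missing data.** With all 60 per arm evaluable, the detectable difference is 884 (t: 895), just under 900.

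**Step 4: smaller differences.** The protocol expects a smaller difference but gives no number, so these values are illustrative. With 54 per arm and alpha 0.017, t-test power is about 20% at 450 steps, 37% at 600 and 57% at 750.

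**Step 5: both arms must succeed first.** One million trials were simulated with 54 per arm, SD 1500 and pairwise t tests. Success was taken as beating control at two-sided 0.025, followed by Arm 3 beating Arm 2 at 0.017. The gains over control are assumptions.

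| Arm 2 gain | Arm 3 gain | Difference | All three tests succeed |
|---|---|---|---|
| 900 | 1350 | 450 | 11.5% |
| 900 | 1500 | 600 | 24.0% |
| 900 | 1650 | 750 | 40.6% |
| 900 | 1800 | 900 | 56.7% |

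In the last row both arms beat control in 79.9% of trials.

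**The case against.** **The 900 steps is a detectable difference, not a forecast.** The protocol sets no number for the second phase. If Arm 3 gained 2000 steps and Arm 2 gained 950, the gap of 1050 would be smaller than Arm 3's gain and still above 945. This stands: the shortfall is conditional on gains near the planning value. However, if the between-arm difference is to be smaller than both arms' gains, 80% power requires Arm 2 above 932 and Arm 3 above 2 × 932 = 1864, more than twice the planning value.

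**Fifty-four per arm is one reading.** The missing-data allowance does not say participants or participant-days, and the primary analysis imputes daily values. At 60 per arm, power at 900 steps just exceeds 80%. This also stands, but it concerns only the margin around 900: at 600 steps, 60 per arm still gives about 42%. Imputation does not restore the information from participants who are lost altogether.

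**Baseline adjustment may reduce the SD.** If 1500 is an unadjusted SD, which the documents do not say, the detectable difference falls to 900 when baseline explains 1 − (900/932)² = 7% of the variance (t: 1 − (900/945)² = 9%). The excess over 900 is therefore fragile. No correlation or adjusted SD is given, though, and 80% power at 600 steps would need an SD of about 1500 × 600/932 = 966 (t: 1500 × 600/945 = 952).

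**The overall success rates depend on fixing Arm 2 at 900.** With the same 900-step gap and Arm 2 at 1200 or 1500, overall success is about 72% or 75%. This is fair, and the simulated figures are illustrative only.

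**No printed number is wrong and no document proposes a no-difference reading.** Both are true. What remains is a claim of power with no calculation behind it and no rule for interpreting a null result.

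**Conclusion.** The concern holds. The statement of power for two phases is supported for the comparisons with control only; nothing in either document supports it for Arm 3 versus Arm 2. That gap does not depend on any assumption.

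Its size does. At 54 evaluable per arm, SD 1500 and two-sided alpha 0.017, 80% power needs 932 to 945 steps, and power at 900 is 75 to 77%. This rests on carrying the first-phase SD and missing-data allowance into the second phase. The miss at 900 steps is small and disappears at a full 60 per arm or with a modest gain from baseline adjustment. At clearly smaller differences, which the protocol leads one to expect if gains over control are near 900, power is well below 80% on either count. The comparisons with control are unaffected. This should be fixed because it governs how the money comparison is read.

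**What to change.** In Protocol 5.1.1 (Accrual) and 9.1, replace the opening sentence with text such as:

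> The study is powered for the two comparisons with control. For Arm 3 versus Arm 2 at two-sided alpha 0.017, 54 evaluable per arm and SD 1500 give 80% power for a difference of about 930 to 945 steps for that test taken alone; the requirement that both arms first beat control lowers the overall chance. The study is not powered for smaller differences, and a non-significant result will not be read as no difference.

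If the sponsor can justify a different evaluable number or a baseline-adjusted SD, state it and recompute. Recompute also if the second-phase alpha changes; at 0.05 the detectable difference with 54 per arm is about 809 to 816 steps.

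The cost is wording only: sample size, alpha, models and participant procedures do not change. The downside is a less favourable power statement for the second phase.

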**A Randomized Trial of Social and Financial Incentives to Increase Physical Activity Among Overweight and Obese Veterans**

**NCT# 03563027**

**April 17, 2020**

## Analysis Implementation Plan – VA Study Trial

### **1. Data Checks**

- a. For each variable (outcome and characteristics/predictor) calculate the following percentiles: 1, 5, 10, 25, 50, 75, 90, 95, 99

### **2. Missing Data**

- a. For outcome variables (Daily Steps) identify missing values at weeks 1-12, 1-4, 5-12, and 13-20
- b. For Steps separately list values that are missing from values that are <1000

### **3. Participant characteristics**

- a. Create Table 1
- b. Estimate baseline measures

### **4. Imputation plan**

- a. Change in mean daily steps
  - i. Model driven approach to run 5 imputations for any missing values or values < 1000 steps
  - ii. Covariates include: study arm, week of study, calendar month, baseline step count, age, gender, race/ethnicity, education, marital status, annual household income, military service period, and BMI

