### **6. Adjusted changes in outcome measures (imputed model is primary; non-imputed is secondary)**

- a. Use generalized linear mixed models (GLIMMIX) with identity link for mean change in daily steps during weeks 5-12 and weeks 13-20.
  - i. Adjusted for baseline steps, calendar month, study arm, participant random effect
- b. Use generalized linear mixed models (GLIMMIX) with logit link (logistic model) for proportion of days achieving step goal during weeks 5-12 and weeks 13-20
  - i. Adjusted for baseline steps, calendar month, study arm, participant random effect
  - ii. Use 1000 bootstrapped samples to find adjusted changes in percentage points with 95% confidence intervals for proportion of days achieving step goals

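### Five imputations and no stated seed leave a borderline primary result dependent on the random draw; more imputations would fix this cheaply (minor)

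*SAP*

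**What the plan says.** Protocol 9.2 commits the primary analysis to multiple imputation ("In our primary analyses, we will multiple imputation for missing data and step values less than 1000") but gives no number of imputations. SAP section 4, item a.i supplies it: "Model driven approach to run 5 imputations for any missing values or values < 1000 steps". Item a.ii lists the predictors, beginning "Covariates include: study arm, week of study, calendar month, baseline step count, age, gender, race/ethnicity", and names no participant effect. The heading of SAP section 6 ranks the analyses: "imputed model is primary; non-imputed is secondary".

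The decision rule is a fixed threshold. Protocol 9.1 tests each of the two intervention arms against control at a two-sided 0.025, and Protocol 9.2 carries this into the analysis: "All hypothesis tests will use a conservative Bonferroni adjustment as described in the power calculation". On the amount of missing data, Protocol 9.1 says only "This calculation assumes a 10% missing data rate".

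Neither document gives a seed, a reason for choosing five, or a check of Monte Carlo error.

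**The concern.** Multiple imputation adds random variation of its own. With M imputations, the pooled estimate scatters around its many-imputation value with variance B/M, where B is the between-imputation variance. B itself is estimated on M − 1 degrees of freedom, which is 4 here. Both quantities enter the p-value. Two analysts who follow the plan exactly on the same data could therefore reach different verdicts when p is close to 0.025.

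The first-phase verdict also decides what follows. Only arms that succeed against control go on to the second-phase comparison with each other, and that comparison bears on the trial's hypothesis that the combined incentives do best.

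**Working it through.** **Inputs from the documents.** 180 participants at 1:1:1 (60 per arm), difference 900 steps, SD 1500, two-sided alpha 0.025 and 10% missing data (Protocol 9.1); M = 5 (SAP 4.a.i).

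**Input not in the documents.** The fraction of missing information (FMI). It is an assumption and is shown as a range.

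**The plan's own power figure.** With 60 × 0.9 = 54 per arm, SE = 1500 × √(2/54) = 288.7 and 900/288.7 = 3.118. Power = Φ(3.118 − 2.241) = Φ(0.876) = 81.0%. The required number is 2 × (2.241 + 0.842)² × 1500²/900² = 52.8, so 53 per arm; 53/0.9 gives 59 per arm, or 177 in total against 180 planned. The stated power of at least 80% reproduces. With the t distribution in place of the normal the figure is 79.9%, which is the reference for the simulated power below.

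**Size of the Monte Carlo error.** Complete-data variance U = 1500² × 2/60 = 75,000 (SE 273.9). Total variance T = U/(1 − FMI), B = FMI × T, and the Monte Carlo SE of the primary difference is √(B/M).

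- FMI 0.01: T = 75,758, B = 758, √(758/5) = 12 steps.
- FMI 0.10: T = 83,333, B = 8,333, √(8,333/5) = 41 steps.

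**Disagreement between two runs.** Simulation of 1,000,000 data sets per cell at the 900-step effect. Each data set receives two independent imputation runs, pooled by Rubin's rules with Barnard–Rubin degrees of freedom (complete-data df 118) and tested at 0.025. Share of trials in which the two runs disagree, per comparison:

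| FMI | When it would arise | M = 5 | M = 20 | M = 50 |
|---|---|---|---|---|
| 0.006–0.014 | scattered missing days, or the listed covariates with no participant effect | 0.9–1.5% | 0.5–0.7% | 0.3–0.5% |
| 0.055 | half whole-participant loss, half scattered; participant effect in the model | 3.6% | 1.7% | 1.0% |
| 0.10 | all whole-participant loss; participant effect in the model | 5.9% | 2.6% | 1.6% |

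Type I error is 2.43–2.51% in every cell. Power at FMI 0.10 is 78.5% / 79.7% / 79.9% for M = 5 / 20 / 50; at FMI 0.01 it differs by at most 0.2 points.

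**Link from missing days to FMI.** A participant-day simulation (56 days, 10% missing, assumed within-participant daily SD 3000, M = 5) gave the following. With arm-based imputation and no participant effect, FMI was 0.011–0.012 and disagreement 0.9–1.4% under scattered, mixed and whole-participant loss alike. With a participant effect, FMI was 0.008 (scattered), 0.053 (mixed) and 0.097 (whole-participant), with disagreement of 1.2%, 3.2% and 6.1%.

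**Where it bites.** Chance that one M = 5 run falls on the other side of 0.025 from the many-imputation p-value:

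| Many-imputation p | FMI 0.01 | FMI 0.10 |
|---|---|---|
| 0.015 | 0% | 18% |
| 0.020 | 3% | 37% |
| 0.030 | 5% | 28% |
| 0.040 | 0% | 9% |

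**The case against.** The strongest reply is that nothing here is an error. Five imputations under Rubin's rules are valid, and nothing in the documents contradicts the choice. That is right, and it is why the point is minor.

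The second reply is that the 6% figure does not describe the plan as written. It needs whole-participant loss and a participant effect that SAP 4.a.ii does not list; with the listed covariates the figure is about 1%. This also stands. The upper figure is conditional and should be read that way.

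Third, safeguards exist. Protocol 5.6.1.6 keeps the arms under code letters until the analysis is agreed to be complete, which limits choosing a seed by its result. A non-imputed model is also planned, and a seed may well be set in program code. These soften the consequence, but the non-imputed model is secondary and coded arms do not reduce Monte Carlo error. A seed alone makes a rerun repeatable while the verdict still rests on one draw of five.

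Fourth, the term model-driven is itself loosely defined, and two analysts may differ more over the imputation model than over the seed. That is plausible, but it is a separate question that neither adds to nor removes this one.

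**Conclusion.** The concern holds and is minor. With five imputations and no stated seed, two faithful runs of the primary analysis would disagree at 0.025 in roughly 1% to 6% of trials per comparison. For a many-imputation p of 0.015 or below, or 0.040 or above, the chance of a switch is nil at FMI 0.01; at FMI 0.10 it is still 18% at p = 0.015 and 9% at p = 0.040.

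The range assumes the 900-step design effect and an FMI of about 0.006 to 0.10. Three limits apply.

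- With no true effect, disagreement is 0.5% to 1.2% for FMI 0.02 to 0.10.
- The chance that at least one of the two primary comparisons switches is about double: 7.0% at FMI 0.05 and 11.4% at FMI 0.10, assuming a shared-control correlation of 0.5.
- The documents do not say whether the 10% rate includes values below 1000 steps, which are also imputed. At an assumed FMI of 0.20 to 0.30 the per-comparison figure would be 11% to 16%, so 6% is not a ceiling.

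The mechanism is certain. Its size depends on an FMI that the documents do not give.

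**What to change.** In SAP 4.a.i, replace five with a larger number for the step-count model, for example 50. Twenty already gives about three quarters of the gain: at FMI 0.10, (5.9 − 2.6)/(5.9 − 1.6) = 77%. State the seed and the software before the analysis, and report the Monte Carlo SE beside the primary estimate.

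For the step-count model in SAP 6.a the cost is two entries in the SAP and some computing time. A real cost arises only in SAP 6.b.ii ("Use 1000 bootstrapped samples to find adjusted changes in percentage points") if the bootstrap is run within each imputed data set: 1000 × 5 = 5,000 logistic mixed-model fits per period now, 20,000 at M = 20 and 50,000 at M = 50. Limiting the larger number to 6.a avoids this. In that case the SAP should say which imputed data sets 6.b uses, for example the first five of the same series.

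### As listed, the primary imputation of daily steps omits the participant effect that the analysis model contains, so the standard error would be too small by an amount that rises with the imputed share

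*SAP*

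**What the plan says.** SAP section 4, item a.i, describes a "Model driven approach to run 5 imputations for any missing values or values < 1000 steps". Item a.ii gives the predictors: "Covariates include: study arm, week of study, calendar month, baseline step count, age, gender, race/ethnicity, education, marital status, annual household income", followed by military service period and BMI. The imputed variable appears to be the daily count, since SAP section 2 names daily steps as the outcome and week and calendar month are among the predictors. Section 4 names no participant effect, no use of the participant's other post-baseline days, no routine and no pooling rule.

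SAP section 6, item a.i, gives the analysis model for change in steps: "Adjusted for baseline steps, calendar month, study arm, participant random effect". The section heading sets the precedence: "imputed model is primary; non-imputed is secondary".

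Protocol 9.2 also calls for imputation ("In our primary analyses, we will multiple imputation for missing data and step values less than 1000") but gives no imputation model. It adds a check: "To test of the robustness of our findings we will also evaluate models using collected data without imputation". SAP section 2, which covers weeks 5–12 among other windows, will show how much is imputed: "For Steps separately list values that are missing from values that are <1000". On expected loss, Protocol 9.1 says only: "This calculation assumes a 10% missing data rate". It gives no unit.

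**The concern.** The analysis model treats days from one person as correlated; the imputation model, as listed, does not. An imputed day is then drawn around the mean predicted from arm, time, baseline and demographics. It lacks the part of that person's deviation which these do not explain. Completed participant means are pulled towards the prediction and vary too little, and the mixed model reads the reduced spread as precision. Rubin's rules do not restore it, because the between-imputation variance comes from a regression that counts every day as independent information.

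The primary tests are at stake. Each of two intervention arms is compared with control at 0.025 so that the pair stays within 0.05. If the standard error is too small, neither level holds and the confidence intervals are too narrow.

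**Working it through.** **1. The plan's own figure.** Inputs from Protocol 9.1: 180 participants in three equal arms, difference 900 steps, SD 1500, two-sided alpha 0.025 (z = 2.241), 10% missing.

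- Power ≈ Φ(900 / (1500·√(2/n)) − 2.241).
- n = 54 (60 × 0.9): 900/288.7 = 3.118, power Φ(0.876) = 0.81 (noncentral t: 0.80).
- n = 60: 900/273.9 = 3.286, power Φ(1.045) = 0.85 (noncentral t: 0.84).
- Required n = 2·(1500/900)²·(2.241 + 0.842)² = 52.8, so 53. Then 53/0.9 = 58.9, so 59 per arm and 177 in all, against 180 planned.

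The stated power reproduces. It fits best if the 10% means participants lost. It does not forecast the share of days to be imputed, and days under 1000 steps are imputed on top of missing ones.

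**2. Approximation.** Let m be the imputed share and R² the part of between-person variance that the imputation covariates explain. In a completed participant mean, the unexplained deviation carries weight (1 − m). With scattered loss the arm difference is essentially that of the observed days, so its true variance is unchanged while the reported variance falls:

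- reported SE / true SE ≈ √(R² + (1 − R²)(1 − m)²)
- actual type I error ≈ 2·[1 − Φ(2.241 × ratio)]

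Results:

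- R² = 0: ratios 0.95, 0.90 and 0.80 at m = 5%, 10% and 20%; type I error 0.033, 0.044 and 0.073.
- R² = 40%, m = 10%: √(0.4 + 0.6 × 0.81) = 0.941; type I error 0.035.
- Second-phase level (0.0167), R² = 0: 0.031 at 10% and 0.056 at 20%.

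The error rises smoothly with m and has no break point.

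**3. Null simulations of the method as listed.** Common to all: 60 per arm, 56 days (weeks 5–12), five imputations by single-level regression, random-intercept analysis, Rubin's rules, missing completely at random. Day-to-day SD, R² and the imputed share are assumptions, since the documents give none of them. With day SD 3000 and between-person SD 1445, the SD of a 56-day mean is √(1445² + 3000²/56) ≈ 1500, the protocol's figure.

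| Settings | Imputed | SE too small by | Error per comparison | Error, either comparison |
|---|---|---|---|---|
| A: day SD 3000, R² 0–40%, week and month trends, 6000 trials | 2% | – | 0.026–0.032 | 0.047–0.058 |
| A | 5% | – | 0.027–0.034 | 0.049–0.063 |
| A | 10% | 4–9% | 0.030–0.041 | 0.056–0.074 |
| A | 20% | – | 0.040–0.066 | 0.073–0.120 |
| B: day SD 2500, person SD 1500, 800 trials | 5% | 4–6% | 0.031–0.038 | – |
| B | 10% | 7–11% | 0.040–0.048 | – |
| B | 20% | 16–19% | 0.061–0.074 | – |
| C: day SD 3000, R² 0 or 40%, no trends, 1500 trials | 10% | 5–9% | 0.035–0.044 | 0.063–0.083 |
| C | 20% | 10–18% | 0.046–0.064 | – |
| D: day SD 3000, 5000 trials | 0% | – | 0.024–0.027 | – |
| D | 5% | – | 0.029–0.033 | – |
| D | 10% | 8–10% | 0.036–0.039 | – |
| D | 20% | – | 0.053–0.066 | – |

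Monte Carlo standard errors per comparison are 0.0015–0.002 in A and about 0.004 in B (√(0.025 × 0.975/1600), two tests per trial). In A, day SD 2000 or 4000 gave the same 10% range, and the mean estimate stayed within about 10 steps of zero throughout. With 18 of 180 participants lost entirely, A gave a reported SE of 269–273 steps against a true SD of 286–294.

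**4. With a participant term.** At 10% imputed, a participant random intercept in the imputation gave 0.022–0.026, and the non-imputed mixed model gave 0.022–0.027. Under the settings of B, the random intercept gave 0.019–0.029 at 10–20% imputed (500 trials).

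**The case against.** The strongest reply is that SAP section 4 is an outline. Its list is worded as open-ended, the model form is not named, and a random effect is not ordinarily called a covariate. That stands. A reader might infer that the sponsor chose single-level imputation. The documents do not show this; they show a list that leaves the term out. But SAP section 6 does name the participant effect in a similar list, and no passage supplies it for the imputation.

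The size also rests on inputs that no document gives. If the covariates explained 60% of between-person variance, a simulation with 10% scattered loss gave 0.029 per comparison and 0.052 for either, near nominal; with whole participants lost it gave 0.035 and 0.064. Rubin's rules are assumed. Days under 1000 steps are selected by their value, and that mechanism was not simulated. All of this stands and limits the figures, not the direction.

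Mitigation is already planned. The non-imputed mixed model will be run and the amount imputed will be listed. An SE error of 4–11% would change only a borderline result, and the parallel analysis could expose that. This softens the problem without removing it, because the affected analysis is the primary one and nothing ties the imputation model to the share found.

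Three stronger readings are tempting but unsupported:

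- **A safe share, or one at which the problem starts.** At 5% the upper values (0.034 and 0.063 in A) are already clear of nominal. At 10% the lowest either-comparison value (0.056) is only modestly above 0.05.
- **The protocol's 10% as the imputed share.** Its unit is not stated.
- **A biased treatment effect.** Under completely random missingness only the standard error is affected.

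**Conclusion.** The point holds conditionally: if daily steps are imputed from the listed predictors alone and pooled by Rubin's rules, the primary standard error is understated. Taking the simulations together, a nominal 0.025 test runs at about 0.03 with 5% imputed, 0.03–0.05 with 10% and 0.04–0.07 with a hypothetical 20%. At 10%, the error across the two comparisons is about 0.056–0.083 against an intended 0.05. These figures assume missingness completely at random and cover R² mainly from 0 to 40%. The actual size is unknown until the imputed share is. Confidence is medium, because the text leaves room for an unstated participant term. The point should still be fixed, since it concerns the analysis given precedence and is cheap to settle.

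**What to change.** In SAP section 4, item a.ii, specify multiple imputation of daily steps with a participant random intercept (two-level imputation) in addition to the listed covariates. Conditioning on the participant's other observed days serves the same purpose; the random intercept is the version simulated here, and it also covers people with no observed days in the window. Name the routine and the pooling rule. If a participant term is already intended, one sentence saying so is enough.

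No new data are needed and no endpoint changes. The cost is a few words in the SAP, a different routine, more computing and wider intervals. At 10% imputed, simulated standard errors were 4–13% larger than with the method as listed, and at most 4% larger than in the non-imputed mixed model. As a bound on the second figure, a 4% larger SE at 54 per arm gives power Φ(3.118/1.04 − 2.241) ≈ 0.775 instead of 0.81. The widening relative to the listed method largely reflects uncertainty that the listed method leaves out.
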